#### 4.4.2. In vitro study

##### Primary Hypothesis/Alternative Hypothesis (H1)

**H1-in vitro:** *Exposure of primary human gingival fibroblasts to hyaDENT BG® (4 mg/mL) enhances cell proliferation, migration, and extracellular matrix production compared to untreated control cells, supporting its role in soft tissue healing and regeneration.*

##### Secondary Hypotheses (H2-H5)

**H2-in vitro:** hyaDENT BG® treatment results in higher cell viability (CellTiter-Blue assay) compared to control.

**H3-in vitro:** hyaDENT BG® induces upregulation of wound-healing-related genes, including COL1A1, COL3A1, TGFB1, TGFB3, PDGFB, FGF2, EGF, relative to untreated control fibroblasts.

**H4-in vitro:** hyaDENT BG® modulates inflammatory mediator expression (IL1A, IL1B, TNF, IL-8) and

MMP activity (MMP1, MMP2, MMP3, MMP8) toward a profile compatible with controlled matrix remodeling.

**H5-*in vitro*:** hyaDENT BG® activates key intracellular signaling pathways involved in cell proliferation and migration (p-AKT, p-ERK1/2, p-p38) as shown by Western blot analysis.

Null Hypothesis ( $H_0$ ): Exposure to hyaDENT BG® does not significantly affect proliferation, migration, ECM synthesis, inflammatory profile, or signaling activity of fibroblasts compared to untreated controls.

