## **6. MATERIALS AND METHODS**

### **6.1. Study outline**

A prospective, experimental, controlled, randomized study will be performed on 30 patients divided into two groups. In the test group, patients will undergo coronally advanced flap surgery combined with connective tissue graft with application of hyaluronic acid. In the control group, patients will undergo the same surgery without the application of hyaluronic acid.

The study will be complemented by an in vitro component in which a sample of the connective tissue graft will be taken from each patient to isolate fibroblast cells, culture them, and evaluate their viability, proliferation, differentiation, and mediation in cell signaling in the presence or absence of hyaluronic acid.

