#### 8.5. RNA analysis by qRT-PCR

For oral fibroblast cells quantitative RT-PCR is used to investigate the expression of COL1A1, COL3A1, TGFB1, TGFB3, PDGFB, FGF2, EGF, IL1A, IL1B, TNF, MMP1, MMP2, MMP3 and MMP8 genes. Procedure: Total RNA from cells treated with HA or growth factor is isolated using the RNeasy Mini Kit. RNA is reverse transcribed and the relative transcripts of the listed genes, normalized to GAPDH, are measured using FastStart Universal SYBR Green Master ROX and primer sequences are shown in the table. Real-time PCR is performed using a 7500 Real-Time PCR system. Data are analyzed using the  $\Delta\Delta C_t$  efficiency method. All samples are run in duplicate.

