## 9.2 In-vitro study

[figure not shown]
It is intended to evaluate the effect of HA preparation, compared to control cells, on oral fibroblast cells (obtained from gingival grafts) regarding the:

1. Viability of primary cells. Ability to adhere and assume a fibroblast-specific fusiform morphology (Fig.1);
2. Proliferative and migratory capacity of the cells;
3. Expression of COL3A1 and TGFB3 genes (characterize wound healing without scarring);
4. Expression of genes encoding growth factors and cytokines involved in wound healing;
5. Expression of MMP2 and MMP3 (matrix metalloproteinases) genes
6. Phosphorylation of Akt, Erk1/2 and p38 kinases.

**Fig. 3:** Scanning electron microscope images (SEM) of primary human PDL cells seeded onto dentin discs in control, HA and HA cl samples. PDL cells seeded in cross-linked HA

demonstrated qualitatively more elongated cell morphology when compared to control and HA.

**Fig 4:** Left image: Neutrophils in humans are recruited by IL-8 to injury sites where they release IL-1α and TNF-α and activate fibroblasts and keratinocytes to facilitate wound healing. Right image: Cellular and molecular interactions at the wound site. Fibroblast proliferation and differentiation into myofibroblasts are essential to produce ECM, collagen and α-SMA. Macrophages release mediators that facilitate angiogenesis in order to nourish infiltrated and newly proliferated cells at the wound site (Komi et al).

**Table 1:** General properties and effects of mast cell-derived mediators in the wound healing process (Komi et al.).

Clinic Rev Allerg Immunol

Table 1 General properties and effects of mast cell-derived mediators in wound healing process		
Mediator	General properties and effects in wound healing process	Ref
TGF- $\beta$ 1	
 
• Profibrotic multifunctional growth factor
 
• Stimulates fibroblast proliferation and matrix formation
 
• Some mast cell mediators including protease and chymase through activation of latent TGF-<math>\beta</math>1 contribute in the regulation of extracellular matrix formation
 
	[56]
TGF- $\beta$ 2	
 
• Is involved in:               
 
1. Marked collagen deposition
 
2. Increasing mechanical strength of regenerated tissue
 
3. Accelerating the rate of wound healing
 
 
 
	[56]

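### Two of the five in vitro hypotheses (H1 and H4) do not match the section 8 assays: IL-8 is not measured, and MMP activity and matrix production would rest on transcripts alone

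*Protocol*

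**What the plan says.** Section 4.4.2 of the protocol sets out five in vitro hypotheses. The primary one, H1, is that the gel "enhances cell proliferation, migration, and extracellular matrix production compared to untreated control cells", and the in vitro null hypothesis repeats the third outcome as ECM synthesis. H2 is that "hyaDENT BG® treatment results in higher cell viability (CellTiter-Blue assay) compared to control". H3 expects "upregulation of wound-healing-related genes, including COL1A1, COL3A1, TGFB1, TGFB3, PDGFB, FGF2, EGF, relative to untreated control fibroblasts". H4 says that the gel "modulates inflammatory mediator expression (IL1A, IL1B, TNF, IL-8) and" "MMP activity (MMP1, MMP2, MMP3, MMP8) toward a profile compatible with controlled matrix remodeling". H5 concerns phosphorylated Akt, Erk1/2 and p38 on Western blot.

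Sections 8.2 to 8.6 describe five assays: CellTiter-Blue for viability, BrdU ELISA for proliferation, Transwell inserts for migration, qRT-PCR, and Western blot. The qRT-PCR covers "expression of COL1A1, COL3A1, TGFB1, TGFB3, PDGFB, FGF2, EGF, IL1A, IL1B, TNF, MMP1, MMP2, MMP3 and MMP8 genes", and its readout is relative transcripts normalised to GAPDH. The Western blot antibodies are against phospho- and total Akt, Erk and p38, plus vinculin.

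Two further aims appear outside the hypotheses. Section 6.1 says the cells will be cultured to "evaluate their viability, proliferation, differentiation, and mediation in cell signaling in the presence or absence of hyaluronic acid". Section 9.2, under its viability item, adds "Ability to adhere and assume a fibroblast-specific fusiform morphology".

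**The concern.** A hypothesis can be supported or refuted only if something planned measures what it names. Here the hypotheses and the assays are fixed in the same document and disagree in three places: IL-8 and MMP activity in H4, and matrix production in H1.

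The H1 gap matters most because it concerns one of the three outcomes of the primary in vitro hypothesis. The protocol does not say which result would count for or against it. The nearest readouts, the two collagen transcripts, are already assigned to secondary H3.

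The in vitro part is meant to explain the clinical findings and add biological plausibility (section 1.2). Followed as written, the IL-8 part of H4 would have no data. The activity and production claims would either stay unanswered or be argued from mRNA, which shows neither enzyme activity nor deposited or secreted matrix.

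**Working it through.** No sample size, alpha or power figure bears on this point. The check sets each construct named in section 4.4.2 against the readouts in sections 8.2 to 8.6.

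| Hypothesis | Named | Readout in section 8 | Gap |
|---|---|---|---|
| H1 (primary) | proliferation | BrdU ELISA (8.3) | none |
| H1 (primary) | migration | Transwell (8.4) | none |
| H1 (primary) | matrix production | COL1A1, COL3A1 transcripts only (8.5) | transcript, not production |
| H2 | viability | CellTiter-Blue (8.2) | none |
| H3 | 7 genes | all 7 in 8.5 | none |
| H4 | IL1A, IL1B, TNF | all 3 in 8.5 | none |
| H4 | IL-8 | not in 8.5 or 8.6 | no data |
| H4 | activity of MMP1, MMP2, MMP3, MMP8 | transcripts of all 4 (8.5) | transcript, not activity |
| H5 | p-Akt, p-Erk1/2, p-p38 | all 3 in 8.6 | none |

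Marker counts:

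- H3 names 7 genes and 7 are on the panel, so 7 − 7 = 0 are missing.
- H4 names 4 mediators + 4 MMPs = 8 markers and 7 are on the panel, so 8 − 7 = 1 is missing (IL-8).
- H5 names 3 phospho-proteins and 3 are blotted, so 3 − 3 = 0 are missing.
- The panel has 14 genes, and 7 (H3) + 7 (H4 without IL-8) = 14. The match is one to one in both directions, so IL-8 is the only named marker with no counterpart.

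By construct, H1 has 2 of 3 outcomes measured directly and the third only through two transcripts. The hypotheses with a gap are H1 and H4, which is 2 of 5.

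Other parts of the protocol point the same way. Section 9.2 lists the MMP readout as gene expression, and only for MMP2 and MMP3, so it differs from H4 both in what is measured and in how many MMPs are covered. The table of mediators reproduced in 9.2 includes the activation of latent matrix metalloproteases as an effect of its own, so the protocol's own material distinguishes presence from activity. The caption of Fig. 4 gives IL-8 a role in wound healing, so its place in H4 fits the stated rationale.

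Outside the hypotheses, nothing in 8.2 to 8.6 describes a marker of differentiation, an adhesion assay or a method of scoring morphology. The electron microscopy images in Fig. 3 show periodontal ligament cells on dentin discs and are not a described method for these graft fibroblasts.

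**The case against.** The strongest reply is that this is mostly wording. Seven of H4's eight markers are measured, including all four MMPs as transcripts, and both collagens are on the panel. Section 9.2 already calls the MMP readout expression, so the protocol does not show an intention to report mRNA as activity. Viability, proliferation, migration and kinase signalling all have direct assays. The in vitro part is complementary to the trial. All of this stands, and it limits the point to H1 and H4. It does not supply IL-8 data, and it does not bring the hypotheses into line with what 8.5 measures.

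A second reply is that 8.5 refers to a primer table that cannot be seen in the text at hand and might include IL-8. That is possible, but the sentence in 8.5 ties measurement to the genes it lists, and IL-8 is not among them. If the table does include it, the list in the text still needs correcting.

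A reader might also infer more than the documents support:

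- **Several hypotheses name unmeasured biomarkers, including differentiation and adhesion.** Only two hypotheses have a gap. Differentiation appears in 6.1 and adhesion/morphology in 9.2, and neither is in any hypothesis. The latter is a descriptive remark under viability with no comparison attached.
- **Nothing is measured for MMPs or matrix.** Transcripts are. Among the named markers, only IL-8 is wholly absent.
- **The planned samples cannot answer the hypotheses.** Section 8.1.3 obtains fibroblasts from every patient, and IL-8 could be run on the same RNA. The gap lies in the listed assays and the wording.

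**Conclusion.** The point holds for two of the five in vitro hypotheses. In H4, one of eight named markers (IL-8) has no assay, and the MMP claim is about activity while the readout for all four MMPs is mRNA. In primary H1, one of three outcomes (matrix production) has only two collagen transcripts behind it, and the null hypothesis carries the same claim. H2, H3 and H5 match their assays. Differentiation and adhesion/morphology are a separate, minor inconsistency between the stated aims and section 8.

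This rests on reading the gene list in 8.5 as complete and on section 8 describing all the planned assays. The effect is confined to what the in vitro part can conclude. The clinical primary endpoint, the randomisation and the sample size are untouched. Correction is worthwhile before the laboratory work starts because it is cheap and determines which mechanistic statements the study can make.

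**What to change.** 1. **IL-8.** Add an IL-8 (CXCL8) primer pair to the panel in 8.5, run on the same RNA, or remove IL-8 from H4.
2. **MMPs.** In H4, replace activity with gene expression. Make the MMP list in 9.2 agree with H4 and 8.5, since it now names two of the four.
3. **Matrix.** In H1, replace the production claim with collagen (COL1A1, COL3A1) gene expression, and make the same change to ECM synthesis in the null hypothesis. Alternatively, remove the item from both and leave the two collagens under H3, which avoids having the same transcripts in a primary and a secondary hypothesis.
4. **Aims outside the hypotheses.** Delete differentiation from 6.1 and the adhesion/morphology remark from 9.2.

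The cost is at most one primer pair on RNA that is being extracted anyway, plus protocol wording. The downside is a narrower mechanistic claim, limited to transcripts for the MMPs and the matrix. If the sponsor wants to keep the stronger claims, section 8 would need protein or activity assays, which is a larger change.

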## 5. STUDY DESIGN

### 5.1. Type and Design of the Study

This is a prospective, randomized, controlled, post-market clinical follow-up (PMCF) clinical trial designed to compare the outcomes of CAF + SCTG with adjunctive hyaDENT BG® application versus CAF + SCTG alone for the treatment of single RT1/RT2 gingival recessions.

The study is planned to last approximately 2 years, including a patient enrolment phase and a follow-up period of 12 months for each participant, starting from the date of surgery. Periodical follow-up visits will be scheduled as outlined in the study flow chart (Figure 2), ensuring standardized clinical measurements, photographic documentation, and patient-reported outcomes collection throughout the study timeline.

During each appointment, among the clinical procedures, several data will be recorded to accomplish the study goals.

[figure not shown]

Figure 2: Study Flow Chart

### 5.1.1. Endpoints

#### 5.1.1.1. Primary Endpoint

**Complete Root Coverage (CRC)** at 12 months, defined as the proportion of treated recession sites presenting Recession Depth (RD) = 0 mm relative to the cemento-enamel junction (CEJ). Measurements will be performed with a CP-15 calibrated periodontal probe by a blinded examiner, using the CEJ as a fixed reference point.

Photographic documentation will be standardized using the same digital camera model, lens, and magnification settings. All images will be taken at a fixed distance with the aid of a custom acrylic stent and include a millimeter scale for calibration. Consistent lighting and angulation will be maintained across all time points to ensure reliable visual assessment of root coverage.

#### 5.1.1.2 Secondary Endpoints

- **Mean Root Coverage (MRC) and Recession Reduction (RecRed)** at 12 months (T7), expressed in millimeters and as a percentage of baseline RD.
- **Clinical Attachment Level (CAL) gain and Probing Depth (PD) reduction** from baseline (T0) to 12 months (T7).
- **Height of Keratinized Tissue (HKT) gain**, measured from the gingival margin to the mucogingival junction (MGJ) at T4 (12 weeks), T5 (6 months), T6 (9 months), and T7 (12 months).
- Periodontal parameters: **Full-Mouth Plaque Score (FMPS), Full-Mouth Bleeding Score (FMBS), and Bleeding on Probing (BOP)** at T4, T5, T6, T7 to evaluate maintenance of periodontal health.
- **Patient-Reported Outcomes (PROMs):**
  - Visual Analog Scale (VAS) for pain, swelling, and discomfort at T1 (3 days), T2 (14 days), and T3 (6 weeks).
  - Oral Health Impact Profile-14 (OHIP-14) questionnaire at the same time points to assess oral health-related quality of life.
  - Number of analgesics and days of medication recorded at T1.
- **Early Wound Healing Score (EHS):** assessed at T1 (3 days), T2 (14 days), and T3 (6 weeks) to monitor soft tissue healing dynamics.
- **Surgical and postoperative complications:** any intraoperative or postoperative complications (e.g., flap dehiscence, graft necrosis, infection) will be recorded in the adverse event log, including clinical management and outcome.
- **Aesthetic outcomes:** standardized intra-oral photographs will be analyzed to calculate the Root Coverage Esthetic Score (RES) at T7 (12 months) using fixed camera-to-subject distance, identical lighting conditions, and reference positioning. **At T7 (12 months), the esthetic outcome will be assessed using the Root Coverage Esthetic Score (RES), as described by Cairo et al. 2009 [34].**
  - The RES system evaluates five parameters:
    - **Gingival margin (GM):** 0 points = failure of root coverage (gingival margin apical or equal to baseline recession), 3 points = partial root coverage, and 6 points = complete root coverage (CRC).
    - **Marginal tissue contour (MTC):** 0 = irregular/flat margin, 1 = scalloped, physiologic contour.
    - **Soft tissue texture (STT):** 0 = scar formation or keloid-like surface, 1 = normal texture without scarring.

- **Mucogingival junction (MGJ) alignment:** 0 = misaligned MGJ, 1 = MGJ aligned with adjacent teeth.
  - **Gingival color (GC):** 0 = color mismatch with adjacent gingiva, 1 = normal, harmonious color.
- The total RES ranges from 0 to 10, with higher scores indicating better esthetic integration and soft tissue harmony.
  - All photographs will be evaluated by a single calibrated examiner blinded to treatment allocation to minimize assessment bias and ensure consistency across all cases. The examiner will undergo a calibration session using reference images prior to study initiation to standardize scoring criteria.

## 5.2. Study Population

The patient population targeted by this clinical trial comprises adult patients ( $\geq 18$  years old) presenting with single RT1 or RT2 gingival recessions in maxillary or mandibular teeth, requiring surgical root coverage with coronally advanced flap and subepithelial connective tissue graft (CAF + SCTG).

Patients must meet **all inclusion criteria** and **none of the exclusion criteria** listed below.

### 5.2.1. Inclusion Criteria

Patients will be considered eligible for enrolment if they meet all the following criteria:

- Age  $\geq 18$  years, in good general health (ASA I or II).
- Presence of a single gingival recession defect classified as RT1 or RT2 according to the Cairo classification, located on a maxillary or mandibular tooth.
- Recession depth  $\geq 2$  mm, with a clearly identifiable cemento-enamel junction (CEJ).
- Presence of at least 1 mm of keratinized tissue at the site of the recession defect.
- No active periodontal disease (probing depth  $\leq 4$  mm and no bleeding on probing at the selected tooth).
- Adequate periodontal support of adjacent teeth.
- Full-Mouth Plaque Score (FMPS  $\leq 20\%$ ) and Full-Mouth Bleeding Score (FMBS  $\leq 20\%$ ) at screening and immediately prior to surgery.

- Tooth vitality confirmed and absence of caries, non-carious cervical lesions, or defective restorations in the area to be treated.
- Patient demonstrates good oral hygiene and is motivated to maintain plaque control throughout the study period.
- Patient is able and willing to comply with all study requirements, including scheduled follow-up visits and completion of patient-reported outcome measures (PROMs).
- Patient has provided written informed consent before any study-related procedure.

### 5.2.2. Exclusion Criteria

- Patients will be excluded from participation if they meet any of the following criteria:
- Uncontrolled systemic diseases or conditions that contraindicate periodontal surgery (e.g., uncontrolled diabetes mellitus ( $\text{HbA1c} \geq 7.0$ ), severe cardiovascular disease, immunodeficiency).
- Pregnant or breastfeeding women.
- History of autoimmune disease or current immunosuppressive therapy.
- Known hypersensitivity or allergy to hyaluronic acid or any component of the investigational product.
- Heavy smokers ( $>10$  cigarettes/day) or users of smokeless tobacco/nicotine products within the last 6 months.
- Untreated periodontal disease or presence of probing depth  $\geq 4$  mm with bleeding on probing at the study tooth.
- Caries, non-carious cervical lesions, root fractures, defective restorations, or endodontic lesions in the study tooth.
- History of mucogingival surgery or previous root coverage procedure at the study tooth.
- Use of systemic antibiotics, corticosteroids, or anti-inflammatory drugs within 3 months prior to surgery (unless considered safe by the investigator).
- Coagulation disorders or current use of anticoagulant/antiplatelet medication that cannot be discontinued for surgery.
- Hormonal disorders significantly affecting wound healing.
- Active acute infections or inflammatory processes in the oral cavity at the time of surgery.

- Any medical, psychological, or social condition that, in the opinion of the investigator, could interfere with study participation or adherence to the follow-up schedule.

Patients may be informed about the study by any member of the department. However, after verifying the inclusion and exclusion criteria, the principal investigator will ultimately validate the patient's inclusion in the study.

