#### **Contraindications:**

hyaDENT BG® must not be used in patients with:

- Autoimmune diseases or those undergoing immunotherapy
- Known hypersensitivity to hyaluronic acid
- Severe allergy predisposition
- Acute inflammatory or infectious processes
- Coagulation disorders or patients undergoing anticoagulant therapy
- Hormonal disorders

There are no clinical data regarding the use of this product in pregnant or breastfeeding women, or in adolescents under 18 years of age.

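### The exclusion criteria omit one of the product's stated contraindications (severe allergy predisposition) and narrow another (hormonal disorders) without giving a reason

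*Protocol*

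**What the plan says.** Section 2.1 of the Protocol, under Contraindications, says that the product "must not be used in patients with" a set of listed conditions. Three entries matter here: "Known hypersensitivity to hyaluronic acid", "Severe allergy predisposition" and "Hormonal disorders". Each is a separate bullet and none carries a qualifier.

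Section 5.2.2 gives the trial's exclusions. Its only allergy item is "Known hypersensitivity or allergy to hyaluronic acid or any component of the investigational product". Its hormonal item is "Hormonal disorders significantly affecting wound healing". It also has a general health item, "Uncontrolled systemic diseases or conditions that contraindicate periodontal surgery", and a closing catch-all for any condition that, "in the opinion of the investigator, could interfere with study participation or adherence to the follow-up schedule".

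Section 5.2 makes a patient eligible who meets every inclusion criterion and no exclusion criterion. Section 7.1 allocates patients 1:1 and opens the envelope only after the flap has been raised. Section 3.1 requires trained clinicians to keep strictly to the instructions for use.

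**The concern.** Both lists are current protocol text and they do not agree. A site that screens correctly against section 5.2 can admit a patient with a severe general tendency to allergy, or with a hormonal disorder judged not to impair healing to a significant degree. Section 2.1 rules the product out for both.

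The timing of allocation makes this more than a drafting matter. Any enrolled patient may be assigned the gel, so suitability for it has to be settled at screening. If a contraindication is noticed only after the envelope is opened, the team must either give a product that the protocol says not to give, or depart from the assigned treatment after randomisation. The first is a patient-safety problem. The second is an avoidable deviation in a trial of 34 patients.

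**Working it through.** The protocol gives no figure on this point, so the check is a comparison of text.

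**Step 1: the two items.**

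| Condition | Section 2.1, Contraindications | Section 5.2.2, Exclusion Criteria | Result |
|---|---|---|---|
| Allergy to hyaluronic acid | "Known hypersensitivity to hyaluronic acid" | "Known hypersensitivity or allergy to hyaluronic acid or any component of the investigational product" | Covered |
| General allergic tendency | "Severe allergy predisposition" | No item | Absent |
| Hormonal disorders | "Hormonal disorders" | "Hormonal disorders significantly affecting wound healing" | Narrowed |

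The allergy exclusion cannot be read as covering the general tendency. Section 2.1 lists hypersensitivity to hyaluronic acid and severe allergy predisposition as two bullets, so the protocol treats them as different conditions.

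**Step 2: does another rule close the gap?**

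- *ASA I or II (section 5.2.1).* This grades general health. It names neither condition and says nothing about suitability for this product.
- *Systemic disease item (section 5.2.2).* "Uncontrolled systemic diseases or conditions that contraindicate periodontal surgery" concerns fitness for the operation, which both arms undergo. It does not concern fitness for the gel.
- *Catch-all (section 5.2.2).* It depends on the investigator's judgement and on interference with participation or follow-up. It may catch such a patient but does not require it.
- *Validation by the principal investigator (section 5.2.2).* This follows a check of the same two lists, so it inherits the omission.
- *Withdrawal (section 5.2.4).* The investigator may withdraw a patient when an exclusion criterion comes to light or a medical condition develops. A pre-existing contraindication that was never an exclusion criterion is not clearly either.
- *Instructions for use (section 3.1).* This is a general commitment on how the product is used. It can stop the gel being applied, but it is not a screening rule.

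None of these makes exclusion mandatory for either condition.

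**Step 3: the remaining contraindications.**

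- Autoimmune disease is covered. Immunotherapy in section 2.1 becomes immunosuppressive therapy in section 5.2.2, which is not the same group.
- Acute inflammation or infection is limited in section 5.2.2 to the mouth at the time of surgery.
- Coagulation disorders are covered. Anticoagulant treatment is excluded only where it cannot be stopped for surgery. This is arguably consistent, since a patient who has stopped is no longer on treatment.

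The allergy and hormonal items are the clearest mismatches, but the lists need reconciling as a whole.

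**The case against.** The strongest reply is that section 5.2.2 never tells anyone to treat a contraindicated patient. The Contraindications list is itself protocol text, and section 3.1 requires adherence to the instructions for use. A patient could pass section 5.2 and still be barred from the gel. That is right. A reader might infer that the protocol authorises contraindicated use, and the text does not support this. What stands is a screening gap: the bar would operate, if at all, after enrolment and possibly after allocation, when acting on it means departing from the assigned treatment.

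Second, the catch-all can reasonably be read to include someone who must not receive the test product, because that person cannot accept random allocation to it. This reading is open to an investigator but is not imposed on one, so it reduces the gap without closing it.

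Third, the hormonal qualifier may be sensible. An unqualified reference to hormonal disorders gives a screener no threshold, and healing is what the product is meant to support. A reader might conclude that the qualifier should simply be deleted. The documents do not support that as a clean remedy. The first exclusion bars only uncontrolled diabetes (HbA1c at or above 7.0) and so leaves controlled diabetes admissible. If diabetes counts as a hormonal disorder, an unqualified exclusion would contradict that item. The narrowing may be defensible, but the protocol gives no defence of it.

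Fourth, expected harm is limited. Known allergy to hyaluronic acid or to a component is excluded, and section 3 reports rare, mild, transient local reactions and no serious device-related events. This stands and bears on severity. It does not justify setting aside a listed contraindication, and the protocol does not use it for that purpose.

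**Conclusion.** The point holds. Section 5.2.2 lacks an exclusion for severe allergy predisposition and narrows the hormonal contraindication without explanation, so a patient contraindicated by the protocol's own text can be enrolled and randomised to the product. It should be fixed. It is an inconsistency in eligibility and patient safety, not a statistical error: no endpoint, power or type I error figure changes.

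Its size cannot be put as a number of patients. A reader might want a probability that such a patient receives the gel. The 1:1 ratio alone does not give one for the trial, because the protocol says nothing about how common these conditions are among candidates. Nor should a reader infer that every other contraindication is matched, since the wording on immunotherapy, acute infection or inflammation, and arguably anticoagulants also differs.

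The conclusion assumes that sites screen against the lists in section 5.2, as that section directs, and that the Contraindications list states the product's restrictions correctly. The instructions for use are not among the documents.

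**What to change.** In section 5.2.2:

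1. Add "Severe allergy predisposition" as an exclusion criterion.
2. For hormonal disorders, do one of two things. Either align the criterion with section 2.1 and state how controlled diabetes is handled, so that it does not conflict with the first exclusion. Or keep the qualifier and justify in the protocol why the narrower criterion is acceptable against the contraindication.
3. In the same amendment, check immunotherapy, anticoagulant therapy and acute infection or inflammation against section 2.1, and either match the wording or explain the difference.

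The cost is a few lines of eligibility text, the matching entries in the screening checklist, and a slightly smaller recruitment pool. The design, sample size calculation and analysis are unaffected.
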